### 7.9.3. Ancillary Safety Endpoint – Adverse Events

#### **Adverse Events – 4 weeks**

##### Hypothesis

Not applicable. This endpoint is to characterize adverse events during the first 4 weeks of elevated night pacing.

## Analysis Methods

Summarization of adverse events by MedDRA preferred term. Summarization may include pertinent subgroups, including all potentially related events and all CV-related events.

## Determination of Subjects for Analysis

All adverse events reported for subjects actively receiving elevated night pacing will be included.

## **Adverse Events – 8 weeks**

### Hypothesis

There are differential rates of adverse event reporting between subjects randomized to receive elevated night pacing and subjects randomized to elevated night pacing OFF. In addition, adverse events for subjects continuing to receive elevated night pacing will be characterized and extended from the AE's collected during the first 4 weeks.

### Analysis Methods

The adverse event reporting rate during the period from week 4 to week 8 in subjects in the ON arm and OFF arm will be compared and characterized.

The Mean Cumulative Function will be used to compare the adverse event reporting rate between the ON arm and the OFF arm. This analysis will be in the framework of the Andersen-Gill model, which is a generalization of Cox's proportional hazard model, comparing the distribution of events between groups and accounts for multiple events within a subject. To execute this analysis, a data set will need to be derived from the data set of all adverse events that occurred in randomized subjects ordered by subject, using SAS code similar to

```
PROC SQL NOPRINT;
  CREATE TABLE Adverse_MCF_Setup AS SELECT pt, trt, randomdt,
    exitdate, aestdt
  FROM A_Adverse
  WHERE ^MISSING(randomdt)
  ORDER BY pt, aestdt;
QUIT;
```

The variables TStart and TStop will be coded as 0 or 1, with the initial value of TStart for each subject equal to the 0, representing the randomization date. TStop will be the number of days until either an event or censor. Each subsequent TStart will be the previous TStop value in days and the corresponding TStop date will be the sum of the value of TStart and the number of days until the next event or censor. That data set will be constructed using SAS code similar to

```
DATA Adverse_MCF;
  SET Adverse_MCF_Setup;
  BY pt aestdt;
  RETAIN prev_stop;
  IF first.pt THEN DO;
    Tstart=0;
  /*  No adverse events - first record*/
  IF MISSING(aestdt) THEN DO;
    Tstop=exitdate-randomdt;
    status=0;
  END;
  ELSE DO;
    Tstop=aestdt-randomdt;
    status=1;
    prev_stop=Tstop;
  END;
  OUTPUT;
END;
ELSE IF ^MISSING(aestdt) THEN DO;
  Tstart=prev_stop;
  Tstop=aestdt-randomdt;
  status=1;
  prev_stop=Tstop;
  OUTPUT;
  IF last.pt THEN DO;
    Tstart=aestdt-randomdt;
    Tstop=exitdate-randomdt;
    status=0;
    OUTPUT;
  END;
END;
RUN;
```

A data set with a single variable trt with two rows with values 0 and 1 (representing the control and treatment arm) will be created and the analysis will then be implemented using SAS code similar to

```
PROC PHREG DATA=Adverse_MCF COVS(aggregate) covm PLOTS(overlay)=MCF;
  MODEL (Tstart, Tstop)*status(0)=trt;
  BASELINE covariates=IN2 out=OUT2 cmf=_all_ / NOMEAN;
```

```
ID pt;  
RUN;
```

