## **7.2. General Methodology**

Medtronic employees or designees will perform all statistical analyses. Additional exploratory analyses of the data may be conducted as deemed appropriate. Data analysis may be carried out throughout the study without having all enrolled subjects completing study required follow-ups.

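### SAP 7.9.3 builds the recurrent adverse-event data set from an undefined AE table: if it holds AE records only, AE-free subjects drop out silently and the ON/OFF rate ratio is biased

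*SAP*

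**What the plan says.** SAP 7.9.3, Adverse Events – 8 weeks, compares "The adverse event reporting rate during the period from week 4 to week 8 in subjects in the ON arm and OFF arm". On method, "This analysis will be in the framework of the Andersen-Gill model", with start/stop intervals per subject and a robust variance.

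The prose gives the source: "a data set will need to be derived from the data set of all adverse events that occurred in randomized subjects ordered by subject". The SQL step selects subject, arm, randomisation date, exit date and AE onset date "FROM A_Adverse", and its only filter ("WHERE ^MISSING(randomdt")) keeps rows that carry a randomisation date.

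The DATA step then opens a branch with "IF MISSING(aestdt) THEN DO", commented "No adverse events - first record". It writes one censored interval from randomisation to `exitdate`.

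The paragraph on subjects for this analysis sets different windows: OFF is counted over all of its follow-up, ON only while night pacing was being delivered. SAP 7.2 adds that "Data analysis may be carried out throughout the study without having all enrolled subjects completing study required follow-ups".

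**The concern.** A rate needs everyone at risk in its denominator. A subject with no AE has no row in a table of AEs, so a data set built as the prose describes contains only subjects with at least one. The AE-free branch shows that the authors meant these subjects to contribute time, but it fires only if the input already has a row with a missing onset date. Nothing in the SAP promises such rows. SAP 7.1.3 mentions analysis data sets built from the enrollment, baseline and randomization forms and does not mention `A_Adverse`.

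If the rows are absent, the program still runs cleanly. The mean cumulative function and the rate ratio then describe subjects selected for having had an AE. This is the one planned between-arm comparison of AE rates in a study whose purpose includes tolerability.

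**Working it through.** **Tracing the printed code**

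1. The SQL filter can remove rows but cannot add any. With AE records only, the AE-free branch is never reached.
2. The block that writes the closing censored interval (`last.pt`) sits inside the branch for second and later rows. A subject with exactly one AE gets the event interval and no time at risk after it, whatever `A_Adverse` contains.
3. Censoring is at `exitdate` in both arms, about 56 days after randomisation (week 4 to week 12). The text asks for weeks 4 to 8 (about 28 days). The subject rule implies about 28 days for ON and 56 for OFF.

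**Inputs.** The plan states no AE rate, rate ratio or event count for this endpoint, so there is no figure of its own to reproduce. From the SAP: 2:1 allocation and 30 paced subjects, so about 20 ON and 10 OFF if all are randomised. Assumed: Poisson counts at a constant rate, with λ the mean AEs per subject over the window.

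**Formulas.** AE-free share = e^(−λ). Mean count among subjects with at least one AE = λ/(1 − e^(−λ)).

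**Equal follow-up, 28 days, AE-free subjects dropped.** The last column is an Andersen-Gill fit to simulated data (16,000 ON, 8,000 OFF) with closing intervals supplied.

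| Rates ON, OFF | True ratio | AE-free ON, OFF | Retained means | Ratio by formula | Model fit |
|---|---|---|---|---|---|
| 0.4, 0.2 | 2.0 | 67%, 82% | 1.213, 1.103 | 1.100 | 1.09 |
| 0.6, 0.3 | 2.0 | 55%, 74% | 1.330, 1.157 | 1.149 | 1.15 |
| 1.0, 0.5 | 2.0 | 37%, 61% | 1.582, 1.271 | 1.245 | 1.25 |
| 0.3, 0.6 | 0.5 | 74%, 55% | 1.157, 1.330 | 0.870 | 0.86 |

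Over 56 days in both arms, the same three true ratios of 2.0 become 1.19, 1.29 and 1.45, and the 0.5 becomes 0.77.

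**Unequal follow-up (ON 28 days, OFF 56), AE-free subjects dropped**

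- No true difference, 0.3 per 28 days in each arm: ON 0.3/(1 − e^(−0.3)) = 1.157. OFF 0.6/(1 − e^(−0.6)) = 1.330 over 56 days, or 0.665 per 28. Ratio 1.157/0.665 = 1.74; model fit 1.73.
- True 0.5 (0.3 against 0.6): OFF 1.2/(1 − e^(−1.2)) = 1.717 over 56 days, or 0.859 per 28. Ratio 1.157/0.859 = 1.35; model fit 1.33.
- True 2.0: model fit 1.97 to 2.03. Both arms then expect the same count over their own windows, so both are truncated equally.

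**DATA step exactly as printed** (single-AE subjects also lose their closing time). With AE records only, a true 2.0 becomes 0.99 to 1.20 under equal follow-up and 2.50 to 3.00 under unequal; a true 1.0 under unequal follow-up becomes 2.89. If `A_Adverse` does hold rows for AE-free subjects, the printed step gives 1.88 to 2.28 for a true 2.0.

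**Everyone kept and closing intervals supplied.** Across all three window choices the model returns 1.96 to 2.04 for 2.0, 0.98 to 1.00 for 1.0, and 0.49 to 0.50 for 0.5. Unequal windows do no harm once the risk set is complete.

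**Planned size.** At rates 0.6 and 0.3 over 28 days, about 20 × (1 − 0.549) = 9.0 ON and 10 × (1 − 0.741) = 2.6 OFF subjects would remain. In 1,500 simulated trials of 20 and 10, with closing intervals supplied, the median ratio is 1.20, against 2.00 with everyone kept.

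**Sensitivity.** With between-subject variation in rates (gamma, variance 1), the 28-day figure for 0.6 against 0.3 is 1.26, and the no-difference case under unequal windows is 1.62.

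**Censoring at exit, taken alone.** Suppose the ON rate is 0.6 while paced and returns to 0.3 after week 8, with OFF at 0.3 throughout. Running both arms to exit gives (0.6 + 0.3)/(0.3 + 0.3) = 1.5 rather than 2.0, even with no subject lost.

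**The case against.** A reader might infer that the data set has no link to the randomised subjects and will certainly drop everyone without an AE. The documents do not support that. `A_Adverse` already carries arm, randomisation date and exit date, so it has been merged with subject-level data. The AE-free branch shows a clear intention to keep these subjects, and the SAP offers its code only as similar to what will be run. This stands, and it makes the loss conditional. It does not settle the matter: a merge that keeps only AE rows yields the same columns and no AE-free subjects, and the prose describes just that source.

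A reader might also infer that the ratio is always pulled towards 1, so a real excess under continued pacing would be hidden. That holds for equal follow-up, which is what the printed code produces. Under the windows in the paragraph on subjects for analysis, the bias can run the other way and suggest harm from pacing where there is none.

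The concern about missing exit dates is narrower than it looks. Protocol 10.15 requires a Study Exit form with a date for every subject, so the date should exist at the final analysis. It may be missing only in analyses before study completion, and the SAP does not say how it is then filled.

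Finally, SAP section 8 requires at least peer review of safety objectives, which might catch the loss. The SAP gives that reviewer no subject count to check against.

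**Conclusion.** The point holds as a conflict between the SAP's prose and its code over an input table that is never defined, not as a demonstrated loss of subjects. If the table holds AE records only, the bias is large: under equal follow-up a true ratio of 2.0 becomes about 1.1 to 1.25 over 28 days, and under the unequal windows a true 1.0 becomes about 1.7.

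Two faults do not depend on what the table holds. Censoring at `exitdate` agrees with neither the week 4 to 8 period nor the on-pacing limit for ON, and subjects with exactly one AE get no closing interval.

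All sizes rest on assumed AE rates (0.2 to 1.0 per subject per 28 days) that are constant over the window. The comparison is ancillary and unpowered, so what is at stake is the reading of the safety data rather than a formal decision. It should be corrected before the analysis is run.

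**What to change.** 1. Build `Adverse_MCF_Setup` by a left join from the randomised-subject list (`pt`, `trt`, `randomdt`, end of observation) to the AE records, so that every randomised subject has at least one row. Correct the sentence naming the source, and define `A_Adverse`.
2. Reconcile the week 4 to 8 period with the arm-specific windows in the paragraph on subjects for analysis. Then replace `exitdate` by the earliest of exit date, end of the analysis window and data cut-off. This also covers subjects still in follow-up.
3. Move the `last.pt` block outside the branch for second and later rows, so that subjects with exactly one AE also get a closing censored interval.
4. Check that the number of distinct subjects contributing a valid interval equals the number randomised in each arm, and report that count.

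The cost is a few lines of SAS and a short SAP revision, with no new data. The join alone is not enough, because items 2 and 3 would remain.

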### Determination of Subjects for Analysis

Rates of adverse events for subjects randomized to OFF will be calculated over the full period of follow-up, while rates of adverse events for subjects randomized to ON will be calculated only during the period that subjects were actually receiving elevated night pacing.

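### The sample Andersen-Gill code in SAP 7.9.3 leaves out the closing interval after a single adverse event and follows ON subjects to study exit, contrary to the section's own rules

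*SAP*

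**What the plan says.** SAP 7.9.3 (Adverse Events – 8 weeks, Analysis Methods) sets out to compare "The adverse event reporting rate during the period from week 4 to week 8 in subjects in the ON arm and OFF arm". Day 0 is randomisation. After an event, the next interval is to run for "the number of days until the next event or censor".

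The source is described as "the data set of all adverse events that occurred in randomized subjects", and the only filter in the set-up query is "WHERE ^MISSING(randomdt". The query selects subject, arm, randomisation date, exit date and AE start date. It selects no pacing-off date.

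The data step treats a subject's first record in one branch and later records in a second, opened by "ELSE IF ^MISSING(aestdt) THEN DO". The row that closes follow-up is inside the second branch. Each censored row uses "Tstop=exitdate-randomdt" in both arms. The prose also says "The variables TStart and TStop will be coded as 0 or 1", although both variables hold day counts.

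Under Determination of Subjects for Analysis in the same section: "Rates of adverse events for subjects randomized to OFF will be calculated over the full period of follow-up". ON subjects count only while they actually receive elevated night pacing. Protocol 14.1.3 states the same rule.

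**The concern.** This is the planned model-based comparison of AE rates between the randomised arms. The printed code departs from the text in two certain ways and one conditional way.

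1. **Closing row.** A subject with exactly one AE record gets no interval after the event, so follow-up is lost because of AE history.
2. **Censoring.** ON subjects stay at risk, and their AEs are counted, after pacing has stopped. Protocol 10.12.1 has pacing OFF by the end of the 8 week visit, and Protocol 10.14 puts exit at the 12 week visit. Under Protocol 10.11, a subject whose pacing is stopped after an abnormal 4 week result is still followed to week 12. For OFF, the text gives two windows: week 4 to week 8, and full follow-up.
3. **Pre-randomisation AEs (conditional).** Protocol 12.1 collects AEs from consent, and the query has no lower date limit. Unless `A_Adverse` has already been filtered, these AEs get negative times.

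At stake are a diluted ON:OFF ratio if there is a real excess on pacing, and AE means and a Mean Cumulative Function plot that do not describe the stated exposure.

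**Working it through.** **Timing, from Protocol Table 5.** Consent precedes randomisation by 0+21 = 21 to 30+35 = 65 days. Nominally, the 8 week visit is day 28 and exit is day 56 after randomisation.

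**Rows produced by the printed data step** (exit day 56, pacing off day 28):

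| Subject | Code gives | Text requires |
|---|---|---|
| No AE | (0,56,0) | (0,56,0); ON (0,28,0) |
| One AE, day 10 | (0,10,1) only | (0,10,1) and a censored row from day 10; ON to day 28 |
| AEs days 10 and 20, OFF | (0,10,1), (10,20,1), (20,56,0) | the same, if OFF runs to exit |
| ON, AEs days 10 and 45 | (0,10,1), (10,45,1), (45,56,0) | (0,10,1), (10,28,0) |
| Two AEs on day 10 | includes (10,10,1), zero length | two events, no zero-length row |
| Only AE day -12 (if unfiltered) | (0,-12,1), invalid | (0,56,0); ON (0,28,0) |

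These results need no assumed rate. The last row depends on how `A_Adverse` is derived.

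**Effect of censoring alone.** If the excess ends with pacing, half of ON follow-up carries ratio R and half carries 1:
- R = 2: (2×28 + 1×28)/56 = 1.5
- R = 3: (3×28 + 1×28)/56 = 2.0
- R = 1: 1.0

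If the excess lasted to week 12, both halves would carry R, and censoring at exit would not bias the ratio.

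**All three departures together.** I simulated Poisson AEs over 28 days before and 56 days after randomisation, with 60,000-300,000 subjects per arm. The ON excess ended at day 28, the same excess applied before randomisation, and rows with a stop time before day 0 were rejected. I then fitted the Andersen-Gill partial likelihood. The OFF rates are assumptions.

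| OFF rate per 28 days | True 1.0 | True 2.0 | True 3.0 |
|---|---|---|---|
| 0.02 | 0.98 | 1.50 | 2.05 |
| 0.1 | 1.00 | 1.56 | 2.07 |
| 0.25 | 0.99 | 1.48 | 1.87 |
| 0.5 | 1.00 | 1.42 | 1.83 |

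A correct build with ON ending at pacing-off returns 1.98-2.04 for a true 2.0 and 2.98-3.01 for a true 3.0. A clean build run to exit gives 1.48-1.51 and 1.99-2.01, so the censoring accounts for nearly all the attenuation. Rejecting negative stop times is itself an assumption. Across other ways of handling those rows, at OFF rates 0.25-0.5, a true 2.0 reads 1.24-1.54.

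**Reported means.** At an OFF rate of 0.25 the code reports an OFF 4-week mean of 0.31-0.34, and at 0.50 it reports 0.57-0.61. At 0.02 the inflation is negligible (0.021).

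**Subjects affected.** Assume 30 randomised 2:1, so 20 ON and 10 OFF. The expected number of ON subjects with an AE counted after pacing stopped is 20×(1 − e^(−rate)): 0.4 at 0.02, 1.9 at 0.1, 4.4 at 0.25 and 7.9 at 0.5.

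**Sampling error.** For a true 2.0 over four weeks, the expected events at rate 0.5 are 20 ON and 5 OFF. The standard error of the log ratio is √(1/20 + 1/5) = 0.50, so the 95% factor is e^(1.96×0.50) ≈ 2.7. At 0.25 the counts are 10 and 2.5 and the factor is about 4.0. It is wider at lower rates. The bias factor at 0.5 is 2.0/1.42 ≈ 1.4.

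**OFF end date.** Once ON is censored at the end of pacing, running OFF to week 8 or to exit gives the same ratio, because only OFF subjects remain at risk afterwards. It changes the OFF curve and count: at 0.25 per 28 days, a mean of 0.25 at week 8 and 0.50 at week 12.

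**The case against.** The SAP offers its code as illustrative, and SAP 8 requires at least peer review for safety objectives. The ON exposure rule is stated correctly in plain words directly below the code, so a programmer who followed it would have to replace the exit date. This stands in part: the code is not the only specification, and a reader who inferred that the SAP has no valid ON rule would be wrong. But the printed step contradicts that rule, the missing closing row is easy to copy, and peer review cannot choose between the two OFF windows.

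A reader might also infer that pre-randomisation AEs are certainly analysed. The documents do not show this. `A_Adverse` is a derived data set: it already carries arm, randomisation date and exit date, and the code expects records with no AE date for subjects without events. An upstream date filter is possible.

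The size depends on assumed rates. High rates overstate the number of subjects affected: the study collects only system-related, programming-related, cardiovascular and serious AEs, and at 0.02-0.1 per 28 days the closing-row and pre-randomisation faults barely move the ratio. The attenuation from censoring persists at low rates, but only if the excess ends with pacing.

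Finally, the endpoint is ancillary and unpowered. Protocol 14 and SAP 6 tie the decision to proceed to 4 week safety and tolerability, so an inference that this code would decide the trial's outcome or create a false safety signal is not supported.

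**Conclusion.** Wrong as written, and worth correcting before analysis. Two faults are certain from the printed code: no closing row after a single AE record, and ON censoring at study exit against the on-pacing rule in SAP 7.9.3 and Protocol 14.1.3. The handling of pre-randomisation AEs is a fault only if `A_Adverse` does not already exclude them. The two OFF windows conflict in the text and must be reconciled.

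For assumed OFF rates of 0.02-0.5 AE per 28 days, with the excess ending with pacing and rows with a negative stop time rejected, the code dilutes a true ratio of 2.0 to about 1.4-1.55 and a true 3.0 to about 1.8-2.1. It creates no excess where there is none. If the excess lasted to week 12, the censoring would not bias the ratio. Sampling error is larger than the bias throughout, so the practical harm is to the descriptive rates and the Mean Cumulative Function plot rather than to a formal conclusion.

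**What to change.** Amend SAP 7.9.3 and record the change in SAP 7.10:

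- Start from all randomised subjects, so that everyone contributes at least one row.
- Define a censor date. For ON, use the earlier of the date pacing was programmed OFF and exit, as the existing rule requires. For OFF, use one end date obtained by reconciling week 4 to week 8 with full follow-up, or exit if earlier.
- Keep AEs with onset after randomisation and up to the censor date. Do not exclude the randomisation day outright: by Protocol 8.4 and Table 7, programming at the 4 week visit leaves ON subjects at 100 bpm until the next 5 am, so AEs starting after that programming belong to ON exposure. State a rule for that day when the onset time is unknown, and add a sensitivity analysis that counts those AEs.
- Write a closing censored row at `last.pt` for every subject, outside the branch for second and later records.
- Separate tied times so that no interval has zero length.
- Delete the statement that TStart and TStop are coded 0 or 1.
- State how `A_Adverse` is derived.

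The cost is SAP code and wording. Study conduct and the Protocol's on-pacing rule do not change; if the reconciliation alters the OFF window, Protocol 14.1.3 should be aligned. Pacing-off dates should be recoverable from the visit and crossover interrogation and Save-to-Media files in Protocol 10.16.

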## 7. Study Design

The REVAMP Clinical Study will be a multi-center, prospective, randomized, single-blinded, clinical feasibility study. Subjects will be randomized in a 2:1 ratio to elevated night pacing ON or elevated night pacing OFF.

[figure not shown]
It is expected that up to 50 subjects may be enrolled to ensure approximately 30 subjects undergo elevated night pacing at approximately 10 sites in the United States to ensure enrollment completion within the pre-specified timeframe.

The REVAMP study will be conducted as a Non-Significant Risk (NSR) IDE study. The REVAMP Research System does not include an investigational device; the ability to program a lower rate of 100 bpm is available in market-released pacemakers, and the Sleep function (which allows a different rate to be programmed for part of a 24 hour clock) is an approved feature in market-released pacemakers that will be used in the clinical study. The study will be conducted in compliance with 21 CFR Parts 11, 50, 56, 812.2(b)(1). This study does not require an IDE submission to FDA.

The Sleep Function will be programmed so that the pacemaker can deliver an elevated pacing rate of 100 bpm during the night for 5 hours and lower the rate during the daytime hours. This is within the FDA-approved programmable parameters of the Sleep Function feature. The associated minimal risk will be minimized as described in Section 11.2. Risk Minimization.

The study will collect the following information: demographics, medical history, medications, standard physical, NYHA class, blood samples to measure NT-proBNP, Troponin and other biomarkers, echo measurements, MN Living with Heart Failure Questionnaire, EQ-5D-5L Questionnaire, 6 Minute Walk Test, implanted device information, device interrogations, save-to-media, adverse events (including death), system modifications, and exit information. The MN Living with Heart Failure Questionnaire was chosen to measure the quality of life for subjects with heart failure, which includes a question on how well the subject is sleeping at night.

See Section 10. Study Procedures. for further detail on study procedures and data collection as well as time-points for data collection.

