### 10.11. Randomization (4 Week Follow-Up)

Subjects will be assigned to a group at random during the randomization visit. Randomization will occur at 4 weeks.

Subjects will be randomized in a 2:1 ratio to the Elevated Night Pacing ON or to the Elevated Night Pacing OFF group.

Sites will receive this randomization assignment from the randomization schedule, which is automatically populated on the eCRF.

Procedures to be performed and data to be collected at Randomization include:

- Physical Assessment (including weight, heart rate, symptoms, and blood pressure)
- Medications
- NYHA Class
- MN Living with Heart Failure Questionnaire
- 6 Minute Walk Test
- Echo\*
- Blood Draw\*\*
- Randomization assignment
- Device Interrogation/ (initial)
- Save-to-Media (initial)
- Device Programming, see Table 7: Programming Recommendations at 4 Week Follow-Up
- Device Interrogation (final) - this needs to be completed at the end of the visit after programming has been completed
- Save-to-Media (final)
- Adverse Events (report new/assess ongoing AEs), Study Deviations, System Modifications, Device Deficiencies, Crossovers (as they occur)

\*The echo must be sent to the Echo Core Laboratory for analysis, with a copy of the echo remaining at the site. Details of the Echo Core Laboratory, type of echo to be performed, and the review process will be provided in an Echocardiography Handbook (provided under separate cover).

\*\* The blood sample must be sent to the Blood Core Laboratory for analysis. Details of the blood core lab and the blood draw process will be provided under separate cover.

For any subject who has an abnormal NT-proBNP, troponin or LVEF measurement as defined in the Safety Assessment (Section 10.19. Assessment of Safety) and the investigator elects to discontinue elevated night pacing, a subsequent visit will be necessary for the elevated night pacing to be programmed OFF if the subject was randomized to the elevated pacing ON arm. The subject should continue to be followed through the 12 week visit.

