### **12.1. Adverse Events**

Adverse Event definitions are provided in Table 10. To ensure that all AEs that are potentially relevant are collected, the following will be collected throughout the study duration, starting at the time of signing the Informed Consent Form:

- All system related AEs
- All programming related AEs
- All cardiovascular related AEs
- All Serious Adverse Events (SAEs), regardless of relatedness

In order to fully understand intolerable symptoms and mitigate any safety concerns about elevated night pacing, for any subject that exits the study because of intolerable symptoms, the enrolling site should report any associated programming related AEs. Reporting of these events to Medtronic will occur on an Adverse Event (AE) eCRF. Documented pre-existing conditions are not considered AEs unless the nature or severity of the condition has worsened.

For AEs that require immediate reporting (see Table 12), initial reporting may be done by phone, fax, or on the eCRF completing as much information as possible. The original completed AE eCRF must be submitted to Medtronic as soon as possible.

Each adverse event must be reported separately. Any medication, whether cardiovascular or not, associated with the treatment of an adverse event must be reported.

Subject deaths are also required to be reported. Refer to Section 12.6. Subject Death for Subject Death collection and reporting requirements.

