## 5. Investigation Plan

### 5.1. Study Design

The REVAMP Clinical Study will be a multi-center, prospective, randomized, single-blinded, clinical feasibility study. Subjects will be randomized in a 2:1 ratio to elevated night pacing ON or elevated night pacing OFF.

It is expected that up to 50 subjects may be enrolled to ensure 30 subjects undergo elevated night pacing at approximately 10 sites in the United States to ensure enrollment completion within the pre-specified timeframe.

[figure not shown]
The REVAMP study will be conducted as a Non-Significant Risk (NSR) IDE study. The REVAMP Research System does not include an investigational device; the ability to program a lower rate of 100 bpm is available in market-released pacemakers, and the Sleep function (which allows a different rate to be programmed for part of a 24-hour clock) is an approved feature in market-released pacemakers that will be used in the clinical study. The study will be conducted in compliance with 21 CFR Parts 11, 50, 56, 812.2(b)(1). This study does not require an IDE submission to FDA.

The Sleep Function will be programmed so that the pacemaker can deliver an elevated pacing rate of 100 bpm during the night for 5 hours and lower the rate during the daytime hours. This is within the FDA-approved programmable parameters of the Sleep Function feature.

The study will collect the following information: demographics, medical history, medications, standard physical, NYHA class, blood samples to measure NT-proBNP, Troponin and other biomarkers, echo

measurements, MN Living with Heart Failure Questionnaire, EQ-5D-5L Questionnaire, 6 Minute Walk Test, implanted device information, device interrogations, save-to-media, adverse events (including death), system modifications, and exit information. The MN Living with Heart Failure Questionnaire was chosen to measure the quality of life for subjects with heart failure, which includes a question on how well the subject is sleeping at night.

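### The interval rule for the week 4–8 adverse-event comparison drops same-day and day-0 events, and a sandwich Wald p-value from it would be unreliable with about 20 ON and 10 OFF subjects

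*SAP*

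**What the plan says.** The hypothesis in SAP 7.9.3 (Adverse Events – 8 weeks) has no direction: "There are differential rates of adverse event reporting between subjects randomized to receive elevated night pacing" and those randomised to OFF. The method is a Mean Cumulative Function in an Andersen-Gill framework. Treatment is the only covariate, "MODEL (Tstart, Tstop)*status(0)=trt", and the procedure call is "PROC PHREG DATA=Adverse_MCF COVS(aggregate) covm PLOTS(overlay)=MCF". That call requests a robust variance aggregated by subject, and `covm` also appears in it. The section gives no test statistic, no significance level, no small-sample method and no rule for an arm without events.

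Time starts at 0 on the randomisation date. For later records, "Each subsequent TStart will be the previous TStop value in days", and the data step printed below that sentence does the same, using differences of dates. Neither the text nor the code deals with equal dates.

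On data collection, Protocol 12.1 requires that "Each adverse event must be reported separately". On size, Protocol 7 plans that "up to 50 subjects may be enrolled to ensure approximately 30 subjects undergo elevated night pacing". SAP 5.1 adds "Subjects will be randomized in a 2:1 ratio to elevated night pacing ON or elevated night pacing OFF", and Protocol 10.11 adds "Randomization will occur at 4 weeks".

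**The concern.** A counting-process record (start, stop] contributes an event only if the subject is at risk just before the stop time. A record whose start equals its stop is in no risk set, so its event disappears without notice.

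The protocol makes such records plausible. Table 9 lists dizziness, palpitations, heart racing and shortness of breath as harms of a single cause. Protocol 8.4 says that any telemetry returns a device with the therapy on to 100 bpm until 5 am. ON subjects can therefore be paced at that rate for the rest of the randomisation day, and day-0 losses could fall more on ON, which would hide harm.

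The robust variance is also a large-sample device. With roughly ten OFF subjects, a Wald test built on it may miss its level, and it breaks down when OFF has no events. The 4-week AE analysis is descriptive, so no other between-arm AE comparison would reveal either fault.

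**Working it through.** **Arm sizes.** About 30 subjects start pacing (Protocol 7). At 2:1 (SAP 5.1) that gives 30 × 2/3 = 20 ON and 30 × 1/3 = 10 OFF. Exits before randomisation at week 4 reduce both. The plan states no AE rate, power or level for this comparison, so there is no figure to reproduce.

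**Lost events.** The SAP data step, run literally with exit on day 56, gives:

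| AE days | Records produced | Lost |
|---|---|---|
| 5, 5, 12 | (0,5], (5,5], (5,12], (12,56] | second AE on day 5 |
| 0, 7 | (0,0], (0,7], (7,56] | AE on day 0 |

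After day 0 the first AE of a date is kept and the rest are lost. With a mean of m AEs per same-day episode the share lost is 1 − 1/m. This is 1 − 1/1.25 = 20%, 1 − 1/1.5 = 33% and 1 − 1/2 = 50%. On day 0 every AE is lost.

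**Wald test.** Assume equal 28-day follow-up and no lost events. Let D1 and D0 be the ON and OFF event totals and y a subject's count. The model then reduces to

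- estimate = log[(D1/20)/(D0/10)]
- robust variance = Σ_ON(y − ȳ_ON)²/D1² + Σ_OFF(y − ȳ_OFF)²/D0²

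A full fit and this closed form agreed on a test data set. The table gives rejection rates with no true difference at an assumed two-sided 5% level, over gamma frailty variance 0–2. Trials with an empty arm count as non-rejections.

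| Assumed AEs per subject | Sandwich Wald, 20 v 10 |
|---|---|
| 0.1 | about 0.4% |
| 0.2 | 1.7–2.0% |
| 0.5 | 4.5–6.0% |
| 1 | 6.7–9.9% |
| 2 | about 7–11% |

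At 200 v 100, for 0.1–1 AE per subject, the range is 4.2–5.7%, so the small arms are the cause.

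**No OFF events.** At 0.1 AE per subject without frailty, P(none in 10) = exp(−10 × 0.1) = 36.8%. With frailty variance φ it is (1 + 0.1φ)^(−10/φ). This gives 1.1⁻¹⁰ = 38.6% for φ = 1 and 1.2⁻⁵ = 40.2% for φ = 2.

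The log hazard ratio then has no finite maximum, but the sandwich standard error stays finite. Take 2 ON subjects with one AE each and none in OFF:

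- The ON term is [2(0.9)² + 18(0.1)²]/2² = 1.8/4 = 0.45.
- The OFF term tends to 1/10 = 0.10.
- The standard error is √0.55 = 0.742.

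The iterations stopped at 10.67 to 19.67 depending on the convergence tolerance. Robust z is therefore 10.67/0.742 = 14.4 up to 19.67/0.742 = 26.5. The model-based p-value is 0.96–0.999. Under the null, the chance that both events fall in ON is (2/3)² = 0.44.

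**Robust score test of the same model.** With D = D1 + D0 and ȳ the pooled mean count:

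- U = D1 − (20/30)D
- V = (10/30)² Σ_ON(y − ȳ)² + (20/30)² Σ_OFF(y − ȳ)²

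U/√V is defined when OFF has no events. Its simulated size is 5.1–5.5% at 0.5–2 AEs per subject, about 5–7% at 0.2 and 2.7–3.9% at 0.1.

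**Power at ON 0.8 v OFF 0.1 AEs per subject, no frailty.** The score test has about 86% and a re-randomisation test 62%. The Wald test has 37% if empty-OFF trials count as non-rejections and 74% if they count as rejections.

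**The case against.** **The SAP prescribes no Wald test.** A reader might infer one at 5% from the robust-variance option, but the SAP names neither a statistic nor a level. This stands. The error-rate part is conditional on how the output is read, and the model itself need not be dropped, since its robust score test behaves acceptably.

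**The empty-arm effect has no fixed direction.** It is tempting to say that an empty OFF arm leaves the test unable to signal harm. The check does not support that: the sandwich p-value may be absurdly small instead. The 37% power figure depends on counting those trials as non-rejections.

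**Inflation needs high AE rates.** Protocol 12.1 collects system-, programming- and cardiovascular-related AEs plus serious AEs. One or two per subject in four weeks may not occur, and near 0.5 the level is about right. This stands.

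**One episode may be one AE.** Table 11 has the investigator diagnose from presenting signs and symptoms, so dizziness with palpitations may be a single report. A reader might infer that half or more of the AEs will be lost, but the documents give no frequency of shared dates. The mechanism stands; its size is unknown.

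**The code is only illustrative.** That does not answer the lost events, because the prose states the same interval rule.

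**The stakes are modest.** The endpoint is ancillary in an unpowered study, and no decision is tied to this p-value. By-arm tolerability and the between-arm NT-proBNP, troponin and LVEF tests also inform safety. This limits the severity, but none of these counts AEs by arm.

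**Conclusion.** The loss of same-day and day-0 AEs holds on the documents as written and needs no assumed AE rate. Only the share lost is unknown: 20% to 50% for assumed means of 1.25 to 2 AEs per same-day episode.

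The error-rate point holds conditionally. If the sandwich Wald p-value is read with at most about 20 v 10 subjects, it is too strict at 0.1–0.2 AEs per subject, about right at 0.5 and too liberal at 1–2. It should not be relied on when OFF has no events. These figures rest on an assumed two-sided 5% level, assumed AE rates and frailty, and equal 28-day follow-up. SAP 7.9.3 does not guarantee equal follow-up, because it counts OFF over the full period and ON only while paced.

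The documents do not show that the Andersen-Gill model is unusable, that a Wald test was chosen, or that most AEs will be lost. The defect is worth correcting in the SAP but does not threaten the study.

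**What to change.** - **Event times.** Add a rule to SAP 7.9.3 that gives every AE a positive interval, applied identically in both arms. For example, add 0.5 day to day-0 events and small increments to ties within a date.
- **Test.** State that the arms are compared by the robust (sandwich) score test of the same model, or by a re-randomisation test on each subject's AE count over a common week 4–8 window, and not by the sandwich Wald test. The common window matters for re-randomisation, because arm-specific follow-up would make the counts non-exchangeable.
- **Reporting.** Give the rate difference with its interval, and keep the Mean Cumulative Function plot as description.

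The cost is a few lines of SAP text and code, with no change to data collection. The score test runs slightly above nominal at about 0.2 AEs per subject (5–7%). The re-randomisation test is conservative with few events (1.0–1.3% at 0.1 AE per subject, 3.5–4.2% at 1.0) and can have less power than the score test.
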